**REC Ref:** 

To identify potential CV which would cause EBV treatment to fail, interlobar fissure completeness (FC) using QCT analysis and bronchoscopic assessment using a catheter-based system called Chartis is performed prior to treatment.  Chartis is performed using a catheter with an inflatable balloon at the distal tip to occlude the main lobar airway. This is connected to a console that measures airflow, pressure and resistance across the catheter.26 Once the target bronchus is occluded, absence of flow after 5 minutes signifies the absence of CV. Chartis has a proven 75 -90% accuracy prediction rate in EBV-treatment response when it determines there is no CV. 27-29 QCT analysis utilises specific automated software to measure FC based on high resolution CT (HRCT) images. The Chartis system is recommended in those with partial FC (80 – 95%) to bolster the confidence of CV assessment but is optional in those with >95% of FC and EBVtreatment is not advocated in those with incomplete fissures (<80%). 24,31

When treated with EBV, approximately 50% of patients achieved the target of ≥15% post-BD FEV₁ increase, 84% achieved the target total lung volume reduction (TLVR) of ≥350mL and 48% achieved the target mMRC dyspnoea score improvement. As not all patients with confirmed negative CV will benefit from the EBV therapy, it is important to ensure that patients are carefully selected for the procedure. Table 1 summarises the current recommendations for patient selection.

Table 1 – Current recommendations for suitability of EBV therapy 			
Criterion	Details		
Symptom limitation	mMRC ≥ 2, 6MWD between 100 – 500m.		
Residual volume >175% predicted and RV/TLC >55%	Thresholds set in line with previous trials.		
Post-BD FEV1 of 15 - 50% of predicted	Thresholds set in line with previous trials.		
No evidence of significant coexistent pulmonary pathology on HRCT	Reversible pathologies should be treated pre-EBV treatment. Exclude in severe bronchiectasis and pulmonary fibrosis. High risk of pneumothorax if bulla present in or adjacent to the target lobe.		
Heterogeneity of disease	Perfusion scan recommended in homogenous disease to target the lobe with low perfusion for EBV treatment.		
Absence of CV in the EBV-targeted lobe	QCT measurement for FC +/- Chartis system.		
Prior surgery	Exclude if prior surgery in ipsilateral lung		

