Proof of principle for the ability of hyperpolarised gas MRI to directly visualise CV was first described by Marshall *et al.* Using a static imaging technique of a single breath-hold of up to 20 seconds, they were able to demonstrate delayed filling of ventilation defects thought to be due to collateral ventilation in four out of 10 COPD patients scanned. Delayed ventilation (DV) could be attributed to other factors such as air trapping and significant peripheral airway obstruction. However, in their cohort of patients, collateral ventilation was more plausible due to the peripheral to central pattern of delayed filling of ventilation defects. Chen *et al.* was able to assess DV using dynamic HPX-MRI in 13 out of 15 COPD scanned and suggested further research to establish dynamic HPX-MRI ability to assess CV.

The aim of this study would be to assess the movement of Xe gas in the lungs using HPX-MRI to determine whether in patients with severe COPD it can reliably detect and measure collateral ventilation.

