### 6. OBJECTIVES AND OUTCOME MEASURES

	Objectives	Outcome Measures	Timepoints
Primary	ventilation on HPX-MRI in	Quantitative and/or qualitative detection of differences in the pattern of ventilation in the two cohorts being investigated:	

Protocol IRAS ID: 346681
HypErpolarised Xenon PuLmonary MRI in the Evaluation for EndobronChial Lung REC Ref:

Volume Reduction Therapy

		a) Those with and without	
		confirmed CV;	
		b) Those who were and weren't successfully treated with EBV.	
Secondary	To describe the physiological changes of the lungs seen on HPX-MRI post-EBV treatment	Quantitative and/or qualitative differences of HPX-MRI findings pre- and post-EBV therapy	Baseline and follow-up

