#### QCT (StratX) - not performed as part of research. Required for eligibility assessment.

This will be performed as part of the clinical work-up. Thin section volumetric CT chest images will be uploaded onto StratX, and its automated analysis will provide data on lung voxel density and FCS. The results will be recorded for this study as part of research data collection.

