### **Chartis** – not performed at baseline visit. Required for eligibility assessment.

This will be performed as part of the clinical work-up. The endobronchial catheter-based system will measure the airflow and resistance of the occluded airway for at least 5 minutes to determine the presence of CV. The results will be recorded for this study as part of research data collection.

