#### 11.2. Description of the Statistical Methods

All baseline characteristics and measures will be summarised overall and by cohort and group, using appropriate summary statistics.

ProtocolIRAS ID: 346681HypErpolarised Xenon PuLmonary MRI in the Evaluation for EndobronChial LungREC Ref:

Volume Reduction Therapy CI: [name]

We will aim to describe the prevalence of DV in patients with COPD being worked up for EBV. We will aim to describe the patterns of ventilation seen on HPX-MRI in patients with COPD who have been successfully treated with EBV and compare these findings with those who have not been successfully treated with EBV and those who have not been treated with EBV.

We will aim to examine the relationship between the presence of DV on HPX-MRI and EBV treatment success. We will also aim to correlate the presence of DV seen on HPX-MRI to the presence of CV following Chartis assessment and FC <95% on StratX. Where possible, we aim to examine the relevance of MRI perfusion to the success of EBV treatment and presence of DV. We will also aim to describe the physiological changes observed on HPX-MRI in those who have undergone EBV treatment and whether these changes are different in those who have been treated successfully to those who have not.

Continuous data, including questionnaire outcomes, will be summarised by group and time point using mean and standard deviation (or median and interquartile range if non normally distributed). Effects on outcomes over time (baseline visit and follow up visit) will be analysed using appropriate statistical models.

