#### 11.3. **Sample Size Determination**

This is an exploratory study assessing the value of a novel imaging technique in the assessment of ventilation in those being considered for EBV treatment.

We plan to recruit 40 patients (20 in each Cohort) over a study period of 24 months. Approximately 20 – 30 patients undergo EBV treatment a year in OUH. As the only additional test required of the participants beyond their clinical investigations in this study is the HPX-MRI which could be done on the same day of their other clinical investigations, we could expect a reasonable (i.e. >50%) uptake to the study. Assuming a 50-60% recruitment rate per year, we estimate recruitment of 12-15 patients to Cohort A per year to a total of 20 patients in 18 months.

More patients will be expected to not meet the stringent criteria for EBV therapy. Recruitment of 20 patients to Cohort B will be achievable quicker than Cohort A given the greater number of patients deemed unsuitable post assessment.

This is a pilot study, and an accurate sample size calculation to determine the value of HPX-MRI is not possible. But from our prior studies, Chen et al., Doganay et al., and the Marshall et al. study, it appears that more than 50% of patients with severe COPD have delayed ventilation (DV) suggesting collateral ventilation(CV). This suggests that if HPX-MRI is to generate a useful signal related to DV/CV in comparison to Chartis and QCT may be detectable, as at least 20 of the 40 patients may have DV/CV.

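### Section 11.2 relates delayed ventilation to collateral ventilation only as yes/no against yes/no; adding the continuous StratX fissure score would cheaply improve precision

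*Protocol*

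**What the plan says.** Section 5 (Background and rationale) ends with the aim of finding out whether, in severe COPD, HPX-MRI is such that "it can reliably detect and measure collateral ventilation". Section 5 also divides fissure completeness into three bands. For the middle one: "The Chartis system is recommended in those with partial FC (80 – 95" per cent). Above 95% Chartis is optional, and below 80% valve treatment is not advocated.

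Section 9.6.3 describes graded reference data. For StratX, "its automated analysis will provide data on lung voxel density and FCS", and the results are recorded for the study. Chartis "will measure the airflow and resistance of the occluded airway for at least 5 minutes" in order to determine whether CV is present, and its results are recorded too.

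Section 11.2 names one association between DV and CV. It will "correlate the presence of DV seen on HPX-MRI to the presence of CV following Chartis assessment and FC <95% on StratX". For graded data in general, "Continuous data, including questionnaire outcomes, will be summarised by group and time point using mean and standard deviation" (or median and interquartile range). The primary outcome in section 6 is wider: "Quantitative and/or qualitative detection of differences in the pattern of ventilation in the two cohorts being investigated", split by whether CV is confirmed and by whether valve treatment succeeded.

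Section 11.3 gives the size: "We plan to recruit 40 patients (20 in each Cohort) over a study period of 24 months". Section 11.1 says that no separate SAP is in use, so section 11 is the whole plan.

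**The concern.** The aim has two parts, detecting CV and measuring it. The named DV–CV analysis addresses only the first. Presence of DV, presence of CV on Chartis and FC below 95% are all binary, so no stated association asks whether more delayed ventilation goes with a less complete fissure. An FC score of 94% counts the same as one of 79%, although section 5 puts those two patients in different bands.

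With at most 40 patients, what the study can deliver is an estimate with usable precision. If the relation is graded, splitting both variables widens the uncertainty around that estimate and leaves the measuring part of the aim without an analysis. Because no SAP will follow, the choice stands unless section 11.2 is changed.

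**Working it through.** **The plan's own figure.** Section 11.3 expects more than 50% of patients to have DV/CV: 0.50 × 40 = 20, which reproduces its figure of at least 20 of 40. No power, effect size or fixed significance level is stated, so there is nothing further to reproduce.

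**Inputs.** From the protocol: n = 40 (20 per cohort), and a DV prevalence near or above one half. Assumed here: two-sided 5%; a graded link, modelled as bivariate normal DV extent and fissure incompleteness with correlation ρ; splits near the median.

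**Information kept (small-effect limit, median splits).**
- One side cut: 2/π = 0.64, so 40 patients act like 40 × 0.64 ≈ 25.
- Both sides cut: (2/π)² = 0.41, so 40 patients act like 40 × 0.41 ≈ 16.

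**Closed-form power at n = 40.**
- Both continuous: Φ(atanh(ρ)·√37 − 1.96). For ρ = 0.4: 0.4236 × 6.083 − 1.96 = 0.617, giving 73%. For ρ = 0.5: 0.5493 × 6.083 − 1.96 = 1.381, giving 92%.
- Both cut: φ = (2/π)·arcsin(ρ), then 20 v 20 with proportions 0.5 ± φ/2. For ρ = 0.4: φ = 0.262, 63.1% v 36.9%, power 38%. For ρ = 0.5: φ = 0.333, 66.7% v 33.3%, power 56%.

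**Simulated power at n = 40 (repeat runs agree to within about 2 points).**

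| ρ | Both continuous (rank correlation) | One side cut (rank test) | Both cut, chi-square | Both cut, Fisher |
|---|---|---|---|---|
| 0.3 | 42% | 30% | 23% | 15% |
| 0.4 | 70% | 51% | 38% | 28% |
| 0.5 | 89% | 73% | 56% | 44% |
| 0.6 | 98% | 90% | 76% | 66% |
| 0.8 | ~100% | ~100% | 98% | 95% |

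Part of the Fisher column is that test's own conservatism and not the effect of splitting; chi-square is the fairer comparison.

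**Uneven splits.** Section 5 cites delayed filling in 4 of 10 patients in one study and DV assessed in 13 of 15 in another. Taking both as DV prevalence, (4 + 13)/(10 + 15) = 68%. With DV split at 68% and FC at 50% or 70%, chi-square power is 36% at ρ = 0.4 and 53–54% at ρ = 0.5, close to the median-split figures.

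**A different shape of link.** Suppose DV occurs in 75% of patients on one side of the FC cut and 25% on the other, with extent otherwise random. Fisher on the yes/no table then has about 84–86% power and the rank correlation about 66–73%, depending on whether DV-absent patients share a score of zero. The ordering reverses.

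**Within a cohort.** In a two-peaked model (cohort means ±1, SD 0.7, overall ρ = 0.5), rank-correlation power within one cohort of 20 is about 24%. For precision, an observed correlation of 0.4 has an approximate 95% CI of tanh(0.4236 ± 1.96/√37) = 0.10 to 0.63 with 40 patients, but tanh(0.4236 ± 1.96/√17) = −0.05 to 0.72 with 20.

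**The case against.** The strongest reply is that the formal objectives in section 6 are to characterise and describe, that the word measure appears only in the background, and that the decision the test would inform is itself yes/no. Section 5 treats Chartis as a threshold test (no flow after five minutes means no CV), and a two-by-two table answers that question directly. This stands as a reason to keep the table and not demote it. It does not explain why a recorded percentage should be left out of the only association named.

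Three stronger readings are tempting, and the documents do not support them.
- A reader might infer that the graded values go unused. Section 11.2 summarises all baseline measures and continuous data by group, and the primary outcome allows quantitative differences on HPX-MRI between those with and without CV. What is missing is narrower: the FC score has no part in the DV–CV association.
- A reader might infer that the analysis loses about half its power. That depends on a correlation the protocol does not give, on both variables being cut, and partly on using Fisher's test.
- A reader might infer that a yes/no table is the least efficient choice. Under a pure threshold link it does better.

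The gain from Chartis is also limited. The work-up lists it as plus-or-minus, section 5 makes it optional above 95% FC, and section 9.6.3 does not say outright that numeric flow or resistance is captured.

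**Conclusion.** The point holds in a limited form. Section 5 aims to detect and measure CV, while the one DV–CV association in section 11.2 is binary on both sides, leaves the continuous FC score out and merges two FC bands that section 5 separates. If the link is graded with a correlation of 0.4–0.5, n = 40 and near-median splits, the cost is roughly 32–33 percentage points of power by chi-square (70 − 38 and 89 − 56). Keeping just one side continuous recovers 13–17 of those points (51 − 38 and 73 − 56). At a correlation of 0.8 the loss is only 2–5 points, and under a threshold link it can reverse. All of this rests on assumed values.

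The study is exploratory, so the practical cost is imprecision and an unaddressed part of the aim, not a failed test. This is a cheap improvement, not a flaw that threatens the study.

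**What to change.** In section 11.2, keep the yes/no table and add beside it:
- the StratX FC score, as a continuous percentage, compared between DV-present and DV-absent patients, with a 95% CI for the difference;
- the rank correlation of DV extent with FC score, with a 95% CI, where extent is scored from the HPX-MRI scans already acquired;
- the same with Chartis flow or resistance, only where numeric values were recorded, stating how many patients contribute.

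Report these overall and within each cohort. The overall figure can partly reflect the A/B split, since Cohort A is selected for no evidence of CV; the within-cohort figures should be labelled descriptive because about 20 patients give a wide interval.

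The cost is a sentence or two of text and no extra patient procedure. The first item needs only data already collected. The second needs a definition of DV extent, which section 11 does not give, and the reading time to score it. There is also one more exploratory analysis to report.

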#### 11.3. **Sample Size Determination**

This is an exploratory study assessing the value of a novel imaging technique in the assessment of ventilation in those being considered for EBV treatment.

We plan to recruit 40 patients (20 in each Cohort) over a study period of 24 months. Approximately 20 – 30 patients undergo EBV treatment a year in OUH. As the only additional test required of the participants beyond their clinical investigations in this study is the HPX-MRI which could be done on the same day of their other clinical investigations, we could expect a reasonable (i.e. >50%) uptake to the study. Assuming a 50-60% recruitment rate per year, we estimate recruitment of 12-15 patients to Cohort A per year to a total of 20 patients in 18 months.

More patients will be expected to not meet the stringent criteria for EBV therapy. Recruitment of 20 patients to Cohort B will be achievable quicker than Cohort A given the greater number of patients deemed unsuitable post assessment.

This is a pilot study, and an accurate sample size calculation to determine the value of HPX-MRI is not possible. But from our prior studies, Chen et al., Doganay et al., and the Marshall et al. study, it appears that more than 50% of patients with severe COPD have delayed ventilation (DV) suggesting collateral ventilation(CV). This suggests that if HPX-MRI is to generate a useful signal related to DV/CV in comparison to Chartis and QCT may be detectable, as at least 20 of the 40 patients may have DV/CV.

#### 11.4. **Analysis populations**

All participants who have completed HPX-MRI scans will be included in the analyses.

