### 3. SYNOPSIS

In this study, we aim to identify and characterise the pattern of ventilation in 2 groups of patients with COPD using hyperpolarised xenon-129 MRI (HPX-MRI): A) patients who have been selected and subsequently undergone lung volume reduction therapy using endobronchial valves (EBV), B) those who have been identified as not eligible for endobronchial lung volume reduction therapy using current selection criteria. We also aim to assess and describe the physiological changes following endobronchial lung volume reduction therapy.

Study Title	Hyp E rpolarised X enon P u L monary MR I in the Evaluation for Endobron C hial Lung Volume Reduct I on T herapy (EXPLICIT)			
Internal ref. no. / short title	EXPLICIT			
Study registration	This study will be re	gistered on the ISRCTN		
Sponsor	Oxford University Hospitals NHS Foundation Trust [name] . Email: [contact]			
Funder	Medical Research Cou	uncil (MRC)		
Study Design	Feasibility/pilot			
Study Participants	Up to 40 patients			
Sample Size	Cohort A – up to 20 patients Cohort B – up to 20 patients			
Planned Study Period	Up to 24 months			
Planned Recruitment period	Aug 2025 – Feb 2027			
	Objectives Outcome Measures Timepoint(s)			
Primary	To characterise the pattern of ventilation on HPX-MRI in those with confirmed CV	Quantitative and/or qualitative detection of differences in the pattern of ventilation in the two cohorts being investigated:	Baseline and follow-up	

Protocol

IRAS ID: 346681 REC Ref:

HypErpolarised Xenon PuLmonary MRI in the Evaluation for EndobronChial Lung

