Bronchoscopic deployment of EBV is the most extensively studied endobronchial LVR technique. The only two U.S. FDA-approved one-way valves currently in clinical use are the Zephyr (duckbillshaped) and Spiration (umbrella-shaped) valve systems. A meta-analysis of all eligible clinical trials investigating the benefits of these two valve systems have found significant improvement in FEV1 (an objective measure of airway obstruction), lung residual volume (RV, an objective measure of lung hyperinflation), 6-minute walk distance (6MWD, an objective measure of exercise capacity) and St. George's Respiratory Questionnaire (SGRQ, a patient-reported measure of quality of life) for at least 6 months when compared with standard medical treatment. 17 The largest multi-centre randomised controlled trial with 190 participants and the longest follow-up period of 12 months to date is the LIBERATE study using the Zephyr valve system. The mean difference between groups in LIBERATE at 12-month follow-up for post-bronchodilator (post-BD) FEV1 in percent change was +17.96%, RV -522 mL, 6MWD +39.31m, SGRQ score -7.05 (lower score indicating better health) and modified Medical Research Council Dyspnoea scale -0.8 points (mMRC, lower score indicating less breathlessness).18 Sustained benefits have been seen in FEV1, RV and 6MWD even after 3 years. 19 Pneumothorax, haemoptysis and post-procedural pneumonia were the most common complications, usually occurring within 6 months of EBV treatment. Endobronchial LVR treatment has also been reported to be an independent positive predictor of survival and reduces the number of COPD exacerbations.

The greatest benefit of EBV therapy in terms of FEV1 improvement is seen in those with heterogenous emphysematous disease and complete lobar fissure seen on quantitative CT (QCT) analysis. Incomplete lobar fissure is associated with interlobar collateral ventilation (CV) which may prevent EBV treatment from working. CV is the passage of air between alveoli through channels outside of the normal airways. Interlobar CV is more prevalent in COPD possibly due to the formation of new channels between lobes as a consequence of lung parenchymal destruction. The presence of interlobar CV allows movement of air from an untreated lobe to the EBV-targeted lobe, subsequently preventing collapse and volume reduction.

IRAS ID: 346681

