Hypercapnia	Exclude unless stable on NIV treatment for at least 3 months		
Clinically stable disease	Exclude if >3 COPD exacerbations requiring hospitalisation despite optimal medical management in the past 12 months		
Suitability for sedation or general anaesthesia and bronchoscopy	Exclude in untreated significant cardiovascular diseases or high risk of complications from general anaesthesia		

Protocol

HypErpolarised Xenon PuLmonary MRI in the Evaluation for EndobronChial Lung Volume Reduction Therapy

CI: [name]

Smoking cessation	To eliminate a contributing factor to disease		
	progression		
Undergone pulmonary rehabilitation and receiving guideline pharmacologic therapy	To optimise medical treatment prior to invasive therapy		
Severe congestive heart failure (left ventricular ejection fraction <40%) or pulmonary hypertension (right ventricular systolic pressure >50 mmHg)	Exclude due to poor outcomes		

Unfortunately, the modalities currently used to assess CV may fail. FC measurements can be under- or overestimated between software used in QCT analysis. The Chartis system may also fail in about 20% of cases. Failure has been attributed to low patient tolerance during bronchoscopy, inaccurate position or inadequate inflation of the balloon, the presence of secretions and false negative measurements.

Because of its 20% failure rate, plus the need for bronchoscopy, a technique that reduces the failure rate and removes the need for bronchoscopy would clearly be of benefit. Hyperpolarised xenon-129 (Xe) is a state-of-the-art, non-invasive, ionising-radiation-free functional imaging modality that is reproducible, quantitative, safe and well-tolerated which involves minimal patient effort. The inhalation of Xe gas imaged using MRI (HPX-MRI) enables direct visualisation of lung structure as it flows and fills the airways and alveoli, mirroring the passage of atmospheric gases. Abnormalities in ventilation, due to airway narrowing or bullae formation for example, can be qualitatively and quantitatively measured. The process of the pro

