At the baseline visit, participants written consent (unless obtained prior to baseline visit), demographics, past medical history, alcohol and smoking history are collected, where possible. They may have their baseline heart rate, blood pressure, respiratory rate and oxygen saturations recorded. These and all trial data will be recorded in the EXPLICIT eCRF. As part of their clinical work-up for EBV therapy, a thin section volumetric CT chest (and its corresponding QCT analysis using StratX software) +/- Chartis assessment, full pulmonary function tests (PFTs), 6-minute walk test (6MWT), mMRC dyspnoea score and SGRQ should have been completed, where possible. If any of these (except PFTs, StratX and Chartis) were not completed as a part of their clinical

assessment before their baseline visit, they shall be carried out during their baseline visit, where possible.

HPX-MRI chest and/or perfusion MRI may be performed at the baseline visit. In the event of a new respiratory condition developed since the clinical CT chest as part of the EBV work-up before the baseline visit, a research low-dose CT may be performed to ensure the lung parenchyma has not changed. This will be justified by a research clinician, e.g. in the event of a new chest infection.

Following their baseline visit, participants who have had undergone EBV therapy may be invited to complete one additional follow-up visit after their first clinical post-procedure follow-up. This follow-up visit should happen at 6 months of their clinical follow-up. All the assessments carried out as part of their EBV clinical work-up (except StratX and Chartis) should have been repeated during their clinical follow-up. If any of these were not completed as part of their clinical assessment before their follow-up visit, they shall be carried out during their follow-up visit, where possible. HPX-MRI Chest and/or perfusion MRI may be repeated as part of their follow-up visit.

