#### 11.7. Procedure for Accounting for Missing, Unused, and Spurious Data.

Complete case analysis will be performed at each time point. Missing data will be excluded.

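### Failed or non-evaluable HPX-MRI scans are counted nowhere, and section 11.4 does not say which visit's scan defines the analysis population

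*Protocol*

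**What the plan says.** - **Population (11.4).** One sentence, with no visit named: "All participants who have completed HPX-MRI scans will be included in the analyses".
- **Missing data (11.7).** "Complete case analysis will be performed at each time point. Missing data will be excluded".
- **No further document.** Section 11.1 states that no separate SAP is in use, so these two rules are the whole plan on this point.
- **Purpose.** The synopsis labels the design "Feasibility/pilot". Section 5 motivates HPX-MRI by the shortcomings of Chartis: "Because of its 20% failure rate, plus the need for bronchoscopy".
- **Scan failure is foreseen.** Section 9.6.3 allows up to four xenon inhalations per visit, partly so that a technically failed scan can be repeated. It gives no failure rate. The objectives and outcomes (section 6) and the methods (11.2) count no failed or unreadable scans.
- **Chartis failures are kept.** Section 8.1 describes Cohort B as including patients ineligible because Chartis was inconclusive or not completed.
- **Treatment failures are named.** Sections 8.1 and 11.2 make unsuccessfully treated patients a comparison group.
- **Who is scanned and followed.** Section 7 is permissive: "HPX-MRI chest and/or perfusion MRI may be performed at the baseline visit". It also leaves inviting treated participants to follow-up as an option, while untreated participants are to be invited. Section 9.7 and Appendix A schedule the scan and the follow-up for everyone.
- **Size (11.3).** "We plan to recruit 40 patients (20 in each Cohort) over a study period of 24 months". At least 20 of the 40 are expected to have DV/CV.

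**The concern.** A feasibility study of a new test should show how often the test gives no usable answer. Under 11.4 a participant whose HPX-MRI could not be completed is outside the only defined population. Under 11.7 a participant whose completed scan cannot be read for DV drops out of the DV analyses as missing. The results would then show how DV behaves among usable scans without saying how often a usable scan was obtained.

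The handling is also uneven. A Chartis assessment that gives no answer leaves the patient visible in Cohort B, whereas an HPX-MRI that gives no answer leaves no trace. Set beside the Chartis failure rate quoted in section 5, this favours the new test.

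The missing visit in 11.4 creates a second risk. If completed scans means both scans, a treated patient with a good baseline scan and no Visit 2 scan is lost from contrast (b), successful against unsuccessful EBV treatment. Section 5 describes the common EBV complications as "usually occurring within 6 months of EBV treatment", so they tend to fall before that visit, and the loss could be related to outcome.

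**Working it through.** **1. The plan's own figure.** Inputs from 11.3: N = 40, DV prevalence 50% (stated as a lower bound).

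0.50 × 40 = 20. This reproduces the plan's figure, which requires all 40 scans to be evaluable.

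**2. Effect of scan failure on that figure.** Let f be the proportion of participants without an evaluable scan. The protocol gives no f, so a range is assumed, with failure unrelated to DV.

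Analysed n = 40 × (1 − f); expected DV cases = 0.50 × n.

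| f (assumed) | Analysed n | Expected DV cases |
|---|---|---|
| 5% | 38 | 19 |
| 10% | 36 | 18 |
| 20% (same as Chartis) | 32 | 16 |

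**3. Effect on DV–CV agreement.** Let a be agreement among evaluable scans. With non-evaluable scans in the denominator it is a × (1 − f), taking every participant to have a CV classification. Values of 75% and 90% are assumed for a.

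- f = 10%: 0.75 × 0.90 = 67.5%; 0.90 × 0.90 = 81%.
- f = 20%: 0.75 × 0.80 = 60%; 0.90 × 0.80 = 72%.

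**4. What counting the failures would give.** With 40 attempted scans (Clopper–Pearson 95% CI):

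- 4/40 = 10% (2.8% to 23.7%)
- 8/40 = 20% (9.1% to 35.6%)

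The interval is wide, but it is an estimate. A set restricted to completed scans contains no scans that were not completed, so it can give none.

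**5. Contrast (b): who could be lost.** Three texts bear on this.

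- Unsuccessfully treated patients are a named group (8.1, 11.2), so an observed failure is analysed.
- Complete-case analysis applies separately at each time point (11.7), so a missed Visit 2 need not delete a baseline scan.
- Success rests on atelectasis, lung function or symptoms (8.1). Section 7 expects these work-up assessments to be repeated at clinical follow-up, and 12.3 has follow-up data taken from the notes.

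A treated patient is therefore lost only if 11.4 requires both scans, or if no clinical outcome exists. The protocol does not settle the former. Requiring both scans would sit badly with section 9.9, which lets participants stop scans, continue data collection and have existing data retained.

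**6. Illustration of that loss (assumed counts).** Take 20 treated and 10 successes, in line with the roughly 50% reaching the FEV1 target in section 5. If m of the 10 failures have no outcome, observed success = 10/(20 − m).

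| m | Observed success | Failures left |
|---|---|---|
| 0 | 10/20 = 50% | 10 |
| 1 | 10/19 = 53% | 9 |
| 3 | 10/17 = 59% | 7 |
| 5 | 10/15 = 67% | 5 |

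With 17 successes and 3 failures, losing 2 failures leaves one. What matters for contrast (b) is the last column, because the success rate is not itself an outcome of the study.

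**The case against.** The strongest reply is that the primary objective is to characterise ventilation patterns, and a pattern cannot be described without a scan. Section 11.4 is worded as inclusion and says completed, not readable. Repeat inhalations reduce technical failure. The study is exploratory with no formal sample size. All of this is fair, and it justifies describing patterns in evaluable scans. It does not justify leaving the others uncounted, because 11.4 is the only population defined and no other text picks them up.

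Four stronger readings are tempting, and the documents do not support them.

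- **That the rules remove treatment failures.** They do not: such patients are a named comparison group, and only those without the required data are at risk. Nor does the protocol say that patients with complications miss Visit 2 or count as unsuccessful.
- **That the study exists to show HPX-MRI fails less often than Chartis.** The Chartis failure rate is rationale in section 5; no objective or outcome makes that comparison.
- **That section 5 gives an HPX-MRI failure rate of 2 in 15.** The cited dynamic HPX-MRI result of 13 out of 15 may mean 13 assessable or 13 with DV, and 11.3 uses the same study to support DV prevalence.
- **That a headline accuracy or EBV success rate will be overstated.** Neither is a planned outcome. Section 11.2 plans to describe patterns and correlate DV with CV.

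The differing wording in section 7 is an inconsistency to reconcile. It is not proof of selective scanning.

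**Conclusion.** The point holds for the scan and conditionally for the treatment contrast. As written, DV prevalence and DV–CV agreement are conditional on a usable HPX-MRI, and the number of unusable ones is reported nowhere. At assumed failure rates of 5%, 10% or 20%, expected DV/CV cases fall from 20 to 19, 18 or 16. Agreement of 75–90% among evaluable scans corresponds to 60–72% of all attempted at 20% failure. These figures rest on assumed rates and on failure being unrelated to DV; no number stated in the protocol is wrong.

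For contrast (b), treated patients without 6-month data may be lost, possibly informatively, if both scans are required or no clinical outcome is recorded. The size of that loss cannot be computed from the protocol. This should be changed: it is cheap, and it affects what the pilot can conclude.

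**What to change.** 1. **Section 11.4.** Define the population as all participants with an attempted baseline HPX-MRI. Report the number and proportion non-evaluable, with reasons and a 95% CI. Give DV–CV agreement twice: for evaluable scans only, and with non-evaluable scans in the denominator.
2. **Sections 11.4 and 11.7.** For contrast (b), include every EBV-treated participant with an evaluable baseline scan, whether or not Visit 2 was attended. Take the outcome from the clinical follow-up record. Report those without an outcome, with a best/worst-case sensitivity analysis. In the illustration with three outcomes missing, success would be bounded by 10/20 = 50% and 13/20 = 65%, and the DV comparison would be repeated under each extreme.
3. **Section 7.** Reconcile its wording on the baseline scan and on inviting treated and untreated participants with section 9.7 and Appendix A.

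The cost is a few sentences, slightly more analysis, and an all-attempted agreement figure that looks less favourable. The clinical follow-up data are already to be collected (12.3).
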